5.3.3.1. Analysis Methods

5.3.3.1.1. Primary Analysis

Shift from the baseline visit in Study 54135419TRD3013 to the maximum postbaseline score pertaining to suicidal ideation or suicidal behavior (i.e., scores 1 to 10) will be summarized.

The maximum score (of scores 1 to 10) assigned to each participant will be grouped into one of three broad categories: No suicidal ideation or behavior (0), Suicidal ideation (1-5), Suicidal behavior (6-10). Participants with only a score of 11, ie. no scores between 1 to 10, will be classified a No suicidal ideation or behavior. Shifts from the baseline visit in Study 54135419TRD3013 to the maximum postbaseline category will be summarized.

A frequency distribution of the scores for the 11 categories and the 3 composite endpoints will be provided at each time point.

For the suicidal ideation score the shift from baseline visit in the 54135419TRD3013 study to the maximum during treatment will be summarized.

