9.2. Sample Size Determination

As no hypothesis is specified for this study, no sample size estimation is performed. Sample size will be driven by pragmatic considerations. It is expected that from 100 to 200 participants will be enrolled in this study.

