9.4.2. Primary Endpoints

For the analysis of adverse events, see Section 9.4.5.

The 10 items of the C-SSRS and the derived endpoints (Suicidal ideation, Suicidal behavior, Suicidal ideation or behavior, Suicidal ideation score) will be summarized as frequency distributions for each assessment during treatment.

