5.3.3. Estimand for C-SSRS

The C-SSRS is a low-burden measure of the spectrum of suicidal ideation and behavior that was developed to assess severity and track suicidal events through any intervention (Posner 2007). It is a clinical interview providing a summary of both suicidal ideation and behavior that can be administered during any evaluation or risk assessment to identify the level and type of suicidality present. The C-SSRS has been used frequently in clinical studies, and is a validated, standard measure for suicidal ideation assessment. Using the C-SSRS, the outcomes will be categorized using the scoring for the 11 categories:

Suicida	Suicidal Ideation (1-5)		
1	Wish to be dead		
2	Non-specific active suicidal thoughts		
3	Active suicidal ideation with any methods (not plan) without intent to act		
4	Active suicidal ideation with some intent to act, without specific plan		
5	Active suicidal ideation with specific plan and intent		
Suicida	al Behavior (6-10)		
6	Preparatory acts or behavior		
7	Aborted attempt		
8	Interrupted attempt		
9	Actual attempt		
10	Suicide		
Non-su	uicidal self-injurious behavior (11)		
11	Non-suicidal self-injurious behavior		

If no events qualify for a score of 1 to 10, a score of 0 will be assigned (0="no suicidal ideation or behavior that can be assessed on the basis of C-SSRS"). A participant with a score of 11 will be considered as not having suicidal ideation or behavior.

Composite endpoints based on the above categories are defined below:

- Suicidal ideation: A "yes" answer at any time during treatment to any one of the five suicidal ideation questions (Categories 1-5) on the C-SSRS.
- Suicidal behavior: A "yes" answer at any time during treatment to any one of the five suicidal behavior questions (Categories 6-10) on the C-SSRS.
- Suicidal ideation or behavior: A "yes" answer at any time during treatment to any one of the ten suicidal ideation and behavior questions (Categories 1-10) on the C-SSRS.

The following outcome is a numerical score derived from the C-SSRS categories. The score is created at each assessment for each patient.

• Suicidal ideation score: The maximum suicidal ideation category (1-5 on the C-SSRS) present at the assessment. Assign a score of 0 if no ideation is present.

Note that missing data should not be imputed.

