Primary Trial Objective: To assess the long-term safety and tolerability of esketamine nasal spray in combination with an SSRI/SNRI in participants who have completed 32 weeks of esketamine nasal spray treatment in Study 54135419TRD3013.

Estimand Scientific Question of Interest: What is the safety and tolerability of esketamine nasal spray in combination with an SSRI/SNRI in participants who have completed 32 weeks of esketamine nasal spray treatment in Study 54135419TRD3013, based on the C-SSRS?

The estimand is defined by the following 5 components:

Study Intervention: esketamine nasal spray in combination with an SSRI/SNRI

Population: participants who have completed 32 weeks of esketamine nasal spray treatment in Study 54135419TRD3013

Variable: Number of participants who Shift from the baseline visit in Study 54135419TRD3013 to the maximum postbaseline C-SSRS score

Summary Measure: frequency distribution

Intercurrent events and their corresponding strategies:

	Name of Strategy for Addressing Intercurrent
Intercurrent Events	Events and Its Description
Discontinuation of (any component of) study	While on treatment: Only C-SSRS values up to
intervention for any reason	the date of the last dose will be used.
Withdrawal from the study	While on treatment: Same as above

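### C-SSRS composites are defined over the whole treatment period but tabulated by visit, and the only whole-period C-SSRS result is a crude maximum, unadjusted for unequal follow-up

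*SAP*

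**What the plan says.** C-SSRS is one of two primary endpoints (SAP 5.3.1). SAP 5.3.3 defines the suicidal ideation composite as a yes "answer at any time during treatment to any one of the five suicidal ideation questions". The behavior composite and the combined composite are built in the same way. Each therefore gives one value per participant. The suicidal ideation score, by contrast, is created separately at every assessment.

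SAP 5.3.3.1.1 then says: "A frequency distribution of the scores for the 11 categories and the 3 composite endpoints will be provided at each time point". Protocol 9.4.2 says that the items and derived endpoints "will be summarized as frequency distributions for each assessment during treatment".

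The whole-period results are shifts to a maximum. The lead one is the "Shift from the baseline visit in Study 54135419TRD3013 to the maximum postbaseline score pertaining to suicidal ideation or suicidal behavior", repeated for three broad categories. The other reads: "For the suicidal ideation score the shift from baseline visit in the 54135419TRD3013 study to the maximum during treatment will be summarized". The estimand states "Summary Measure: frequency distribution" and uses values up to the last dose. C-SSRS sensitivity and supplementary analyses are marked not applicable.

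Elsewhere the SAP uses person-time: for TEAEs (5.3.2), the relapse-free endpoint (5.4.1.2) and vital-sign abnormalities (5.6.3.2). Section 5.7.8 repeats the primary endpoints by subgroup, including Region.

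**The concern.** There are two separate problems.

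**Definition against table.** A variable that means yes at some point on treatment cannot be read off at Week 20. One programmer could carry a yes forward, giving a series that never falls within a participant. Another could tabulate the yes or no of that rating. The two tables would carry the same label and mean different things.

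**Crude maximum over unequal follow-up.** The more ratings a participant has, the higher the maximum tends to be at the same underlying risk. Participation lasts up to 104 weeks but ends for a whole country once the product is accessible there (SAP 1.2). It also ends individually, for example when the investigator sees no further benefit. A shift count therefore has no fixed time horizon. Between regions, or against another study, a difference could reflect observation time alone. The shift also starts at TRD3013 baseline, so a positive rating in the parent study counts the same as one in the second extension year. TEAEs get an extension-only supplementary analysis (SAP 5.3.2.1.3); C-SSRS does not.

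**Working it through.** There is no plan figure to reproduce: "As no hypothesis is specified for this study, no sample size estimation is performed". What follows illustrates size, with assumed hazards.

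**Inputs**
- Parent-study time: 32 weeks for everyone. SAP 5.3 uses data from both studies, and the shift starts at TRD3013 baseline.
- Extension time: up to 104 weeks (SAP 1.2). Exit at Week 24 is an assumed early departure.
- Weeks per year: 365.25/7 = 52.18.
- Hazard h of a first positive rating: assumed constant at 1, 5, 10 or 20 per 100 person-years. The documents give no rate. Protocol 2.2.3.4 reports suicidality-related events at about 1% to 5% across Phase 2 and 3 TRD studies, without a common follow-up time.

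**Step 1: one participant.** P(ever positive) = 1 − exp(−h × weeks/52.18), with 32 + 24 = 56 weeks or 32 + 104 = 136 weeks.

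| h per 100 person-years | Exit Week 24 | Exit Week 104 | Ratio |
|---|---|---|---|
| 1 | 1.07% | 2.57% | 2.4 |
| 5 | 5.22% | 12.22% | 2.3 |
| 10 | 10.18% | 22.94% | 2.3 |
| 20 | 19.32% | 40.62% | 2.1 |

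**Step 2: the cohort.** If a share f leaves at Week 24 and the rest at Week 104, then P = f × P(56) + (1 − f) × P(136). At h = 5:
- f = 0.2: 0.2 × 5.22 + 0.8 × 12.22 = 10.8%
- f = 0.8: 0.8 × 5.22 + 0.2 × 12.22 = 6.6%
- Ratio: 10.82/6.62 = 1.6

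At h = 1, 10 and 20 the pairs are 2.3% against 1.4%, 20.4% against 12.7%, and 36.4% against 23.6%. Protocol 9.2 says: "It is expected that from 100 to 200 participants will be enrolled in this study". At h = 5, that gives 10.8 to 21.6 ever-positive participants in the first case and 6.6 to 13.2 in the second.

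**Step 3: the rate.** Under a constant hazard, mean person-time to first event or exit is P/h. At h = 5 this is 0.1082/0.05 = 2.16 years for f = 0.2 and 0.0662/0.05 = 1.32 years for f = 0.8. Events divided by person-time give 5.0 per 100 person-years in both cases. This equality follows from the constant-hazard assumption.

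**Extension ratings only, for reference.** With 4-weekly ratings there are 24/4 = 6 by Week 24 and 104/4 = 26 by Week 104. If each rating has an independent chance p of being positive, 1 − (1 − p)^k gives 5.9% and 23.0% at p = 1%, and 11.4% and 40.9% at p = 2%. The ratios are 3.9 and 3.6. They do not describe the planned table, which also includes the parent-study ratings.

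**The case against.** The case against is substantial, and much of it stands.

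- **The by-visit table does not create the follow-up dependence.** A reader might infer that it does. A per-assessment frequency does not accumulate; its limitation is the changing set of participants still on study. The dependence comes from the shift to the maximum.
- **The intended reading is fairly clear.** Protocol 9.4.2 speaks of each assessment, and the Schedule of Activities uses the Since Last Visit form. Ever-counts can largely be recovered from the shift tables: maximum 6-10 for behavior, maximum 1-10 for either, and a maximum ideation score of at least 1 for ideation. The first fix is therefore close to a clarification. Rates and timing still cannot be recovered.
- **A 3.6- to 3.9-fold effect is not supported for the planned analysis.** That range needs extension ratings alone and independence within a person. Positive within-person correlation would reduce it.
- **Suicidality is not wholly without rates.** Each TEAE, including suicidal ideation and suicide attempt, gets an incidence rate (SAP 5.3.2.1.1), and suicidality is an AE category of special interest. The gap concerns C-SSRS, which is a separate, systematically rated primary endpoint.
- **No 2-year risk is understated and no test is biased.** The study is single-arm, without a hypothesis, and the estimand is explicitly while on treatment. The plan claims no 2-year C-SSRS risk.
- **A rate has weaknesses too.** Protocol 5.2 excludes Week 32 C-SSRS items 4 and 5 but not items 1 to 3, so a first positive after Day 1 may be persisting ideation. Censoring may also be informative: lack of benefit leads to withdrawal, and suicidality prompts consideration of stopping (Protocol 8.2.5). The fix has to deal with both.

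**Conclusion.** The point holds as two limited findings. First, the definition and the by-visit table do not fit together, and one sentence would settle it. Second, the only whole-period C-SSRS result is unadjusted for observation time, although the SAP adjusts for it in three other places and plans Region tables where follow-up may differ because of local access.

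Under assumed constant hazards of 1 to 20 per 100 person-years, with the parent-study weeks counted, the effect is about 2.1- to 2.4-fold for an individual leaving at Week 24 rather than Week 104. At 5 per 100 person-years it is about 1.6-fold for a cohort moving from 20% to 80% early leavers. The actual size depends on the real exit pattern and hazard, which the documents do not give.

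The consequence is for interpretation and for regional or cross-study comparison. This is a change that should be made, but it does not invalidate the analysis.

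**What to change.** 1. In SAP 5.3.3 and 5.3.3.1.1, define the composites in the by-visit tables per assessment (yes at that rating), in line with Protocol 9.4.2. Report the ever-composites once per participant.
2. Add one TRD4010 table for suicidal ideation, suicidal behavior, and either: number with at least one positive rating after Day 1, and rate per 100 person-years with 95% CI. Person-time runs from Day 1 to the first positive rating or the last on-treatment C-SSRS, no later than the last dose. The Poisson model with log time at risk as offset, already specified for TEAEs, can be reused.
3. Split that table by Day 1 status (the TRD3013 Week 32 rating), or limit each composite to participants negative for it at Day 1, so that persisting ideation is not counted as new.
4. State beside the estimates that discontinuation for lack of benefit or suicidality may be informative censoring.

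Kaplan-Meier proportions at Weeks 52 and 104 are optional. The cost is a wording change and one extra table from data already collected, plus its repeats across the planned subgroups.

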5.3.3.1.2. Sensitivity Analysis

Not applicable

5.3.3.1.3. Supplementary Analysis

Not applicable

5.4. Secondary Endpoint(s) Analysis

5.4.1. Relapse

5.4.1.1. Definition

A participant is defined as a remitter at a given time point if the MADRS total score is ≤ 10 at that time point.

A relapse is defined by any of the following:

- a) Worsening of depressive symptoms as indicated by MADRS total score ≥22 confirmed by 1 additional assessment of MADRS total score ≥22 within the next 5 to 31 days. The date of the second MADRS assessment will be used for the date of relapse.
- b) Any psychiatric hospitalization for
 - a. worsening of depression
 - b. suicide prevention or due to a suicide attempt

For any of these events, the start date of hospitalization will be used for the date of relapse.

c) Suicide attempt, completed suicide, or any other clinically relevant event determined per the investigator's clinical judgment to be indicative of a relapse of depressive illness, but for which the participant was not hospitalized. The onset of the event will be used for the date of relapse.

In case more than 1 of the relapse criteria are met, the earliest date will be defined as the date of relapse for that participant.

The secondary endpoint is no relapse until the end of the prospective observation period at Week 104 visit (or end-of-study) visit, and no discontinuation of (any component of) study intervention within group of subjects who are in remission at Week 8 visit of Study 54135419TRD3013.

To be aligned with ESCAPE-TRD study, for subjects who do not have an available MADRS result at the Week 8 visit but did not discontinue study intervention or withdraw from study before Week 8, LOCF of MADRS will be applied at Week 8.

5.4.1.2. Analysis Methods

The efficacy analysis of data will be based on the Safety/Efficacy analysis set.

The proportion of subjects with the secondary endpoint (as defined above) will be estimated together with 95% Clopper-Pearson confidence interval. The incidence rate of subjects with the secondary endpoint (as defined above) will be estimated together with 95% confidence interval. The incidence rate is defined as the number of subjects who achieve the secondary endpoint divided by the time at risk. Time at risk is defined as time from Week 8 visit in Study 54135419TRD3013 until last visit date. The 95% confidence interval of the incidence rate will be calculated based on a Poisson model with achievement of secondary enpoint as dependent variable, an intercept and log (time at risk) as offset.

The remission time point is the first time point at which the participant is in remission. This analysis will only include participants for whom the remission time point is before or at Week 32 of Study 54135419TRD3013. Time to first relapse (from remission time point) will be analyzed by the Kaplan-Meier method. Time to relapse will be summarized with median, 25th and 75th percentile (if estimable). Confidence intervals of 25th, 50th, and 75th percentile of time to relapse will also be provided.

A frequency table of the number of relapses for subjects in remission at Week 8 of Study 54135419TRD3013 will be made. A frequency table of the number of relapses for subjects in remission at any time point during Study 54135419TRD3013 will be made. A frequency table of the number of relapses for subjects who were not in remission during Study 54135419TRD3013 but who are in remission at any time point during Study 54135419TRD4010 will be made

The relapse narratives of relapses during Study 54135419TRD4010 will be listed.

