7.2. Participant Discontinuation/Withdrawal From the Study

A participant will be withdrawn from the study for any of the following reasons:

- The participant discontinues study intervention (see Section 7.1)
- Esketamine nasal spray becomes accessible in an individual's local country
- Lost to follow-up
- Withdrawal of consent
- Death

When a participant withdraws before study completion, the reason for withdrawal is to be documented in the eCRF and in the source document. If the reason for withdrawal from the study is withdrawal of consent then no additional assessments are allowed.

Refer to Section 4.4 for study completion definition for participants.

Withdrawal of Consent

If a participant is unable to return for scheduled visits, it does not necessarily constitute withdrawal of consent. Alternate follow-up mechanisms that the participant agreed to when signing the consent form apply, as local regulations permit.

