Study participation will continue for up to a maximum of 2 years (104 weeks), or until esketamine nasal spray becomes accessible in the participant's local country, whichever occurs first. Participants will have access to esketamine nasal spray for a maximum of 2 years during this study. If esketamine nasal spray becomes accessible locally before the 2-year endpoint, then participants will be considered as having completed the open-label extension study and will be switched to a commercially available supply if in the opinion of the treating physician, the participant continues to benefit from treatment and the participant wishes to continue the esketamine nasal spray treatment. Once esketamine nasal spray becomes accessible in a given country, all participants in the long-term extension study will be discontinued at all sites in that country. Study site personnel will notify participants of study termination and schedule an end-of-study visit with each participant.

Randomization

Since this is an open-label extension to Study 54135419TRD3013, no randomization is performed.

Informed consent may be obtained from participants at any time in the 4 weeks before Day 1 (ie, at or after Week 28 visit in Study 54135419TRD3013). Day 1 of this study will be the day of the first esketamine nasal spray dose or Day 1 will be the date of informed consent.

CONFIDENTIAL – FOIA Exemptions Apply in U.S.

Treatment exposure

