5.2. Participant Dispositions

The number of screened participants and reasons for screen failure will be summarized overall.

The number of participants in the following disposition categories will be summarized throughout the study:

- Participants enrolled
- Participants who received study intervention
- Participants who completed, terminated and reasons for termination from the study: if the reason for trial discontinuation is Withdrawal by Subject, the specific reason will also be summarized.

A participant will be considered to have completed the study if he or she has completed assessments at Week 104, or is discontinued from the study and completes end-of-study assessments when commercial esketamine nasal spray becomes accessible in the participant's local country and the study is terminated in the local country.

A listing of participants will be provided for the following category:

• Participants who were enrolled yet did not receive study intervention.

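### The crude relapse-free proportion gives early market-access exits the same weight as 104 weeks of follow-up, so it is not a Week 104 figure; add a fixed-week Kaplan-Meier estimate

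*SAP*

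**What the plan says.** SAP 5.4.1.1 defines the endpoint in two parts. The first concerns relapse: "The secondary endpoint is no relapse until the end of the prospective observation period at Week 104 visit (or end-of-study) visit". The second adds a condition on staying on treatment and names the analysis group, where the week is counted in the parent study, TRD3013: "and no discontinuation of (any component of) study intervention within group of subjects who are in remission at Week 8 visit". For the estimator, SAP 5.4.1.2 states: "The proportion of subjects with the secondary endpoint (as defined above) will be estimated together with 95% Clopper-Pearson confidence interval".

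The same section plans two other summaries:
- An incidence rate: the number of subjects achieving the endpoint, divided by time from the parent Week 8 visit to the last visit.
- A Kaplan-Meier analysis of time to first relapse, from first remission, in participants whose first remission is at or before parent Week 32. It is summarised by quartiles.

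Follow-up in the extension ends at 104 weeks or at local market access, whichever is first. On access, SAP 1.2 says "then participants will be considered as having completed the open-label extension study", and also that "all participants in the long-term extension study will be discontinued at all sites in that country". SAP 5.2 counts as a completer someone who "is discontinued from the study and completes end-of-study assessments when commercial esketamine nasal spray becomes accessible". Protocol 7.2, under "A participant will be withdrawn from the study for any of the following reasons", includes the entry "Esketamine nasal spray becomes accessible in an individual's local country".

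**The concern.** The end-of-study alternative in the endpoint gives each participant a personal horizon. Someone who leaves relapse-free at Week 10 because of a local launch and someone relapse-free at Week 104 add the same amount to the numerator. The first person has had far less time to relapse or stop treatment.

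Access exits are built into the design. Entry requires that commercial supply is not accessible, and Protocol Appendix 3 (Country Selection) limits the study to countries where launch or other access is intended. A reader who takes the proportion as a two-year relapse-free rate would be reading a mixture that shifts with launch dates.

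**Working it through.** **No planned figure to reproduce.** The SAP states no expected relapse, discontinuation or access rate and no sample-size calculation. What follows illustrates size only.

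**From the documents.** Extension follow-up is up to 104 weeks (2 years, taking 52 weeks as a year). Parent Week 8 to Day 1 at parent Week 32 is 24 weeks.

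**Assumed.** Constant hazards: relapse r and other discontinuation d per year, with h = r + d. A share f exits for access, unrelated to outcome and uniformly over Weeks 4 to 104. A relapse between parent Week 8 and Day 1 counts as failure in the crude proportion. s is the share of enrolled Week 8 remitters with no such relapse.

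**Formulas.**
- Composite at a full 104 weeks: s·exp(−2h).
- Mean success at an access exit: M = [exp(−4h/52) − exp(−2h)] / [h·(2 − 4/52)].
- Crude proportion, exits as successes: s·[f·M + (1 − f)·exp(−2h)].
- Excess: s·f·[M − exp(−2h)].

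**Worked case: r = 0.3, d = 0.1, s = 1.** exp(−0.8) = 0.449. M = (0.970 − 0.449) / (0.4 × 1.923) = 0.677.

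| Share exiting for access | Composite at 104 weeks | Crude proportion | Excess, points |
|---|---|---|---|
| 0.10 | 44.9% | 47.2% | 2.3 |
| 0.25 | 44.9% | 50.6% | 5.7 |
| 0.50 | 44.9% | 56.3% | 11.4 |

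If pre-Day 1 relapsers enrol, both columns shrink by s. With all of them enrolled, s = exp(−0.3 × 24/52) = 0.871, and the last row becomes 39.1% against 49.0%.

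**Range.** Taking r = 0.15, 0.3, 0.5; d = 0, 0.1, 0.2; and none, half or all pre-Day 1 relapsers enrolling, the excess is 1.1 to 2.7 points at f = 0.10, 2.8 to 6.9 at f = 0.25 and 5.5 to 13.7 at f = 0.50.

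**Second parametrisation.** Let 30% fail by Week 104, with exits uniform over Weeks 0 to 104. Success at exit averages 0.30 / 0.357 = 0.841. With half exiting, the proportion is 0.5 × 0.700 + 0.5 × 0.841 = 77.1%, against 70.0%. The direction and rough size are the same.

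**The planned rate.** It puts successes over time, so shorter follow-up raises it. If nobody fails, it is 52/(24 + 104) = 0.41 per year when all are followed for 104 weeks, and 52/(24 + 52) = 0.68 per year when all leave at Week 52. In the worked case it goes from 0.449/2.274 = 0.20 per year with no access exits to 0.563/1.854 = 0.30 with half.

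**The planned Kaplan-Meier analysis.** It counts relapse only, uses remission by Week 32 instead of at Week 8, and lists percentiles with no value at Week 104. Its origin also precedes enrolment. At r = 0.3 with remission at Week 8, the 25% quartile is −ln(0.75)/0.3 × 52 = 50 weeks unconditionally, but 50 + 24 = 74 weeks if no pre-Day 1 relapser enrols.

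**The case against.** The open horizon is deliberate. The protocol objective and SAP 1.1 both allow end-of-study as the alternative to Week 104, and the crude proportion estimates that. This stands: a Week 104 value is an additional and more interpretable quantity, and the planned proportion is not an arithmetical error.

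Protocol 9.4.1 also plans Kaplan-Meier curves, so a time-adjusted description of relapse will exist. This stands in part: the curve can be read at any time from remission, but it is not the composite, the Week 8 set or the Day 1 origin.

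A reader might go further and infer that access exits could equally be scored as failures, because SAP 1.2 and 5.2 call them discontinued and Protocol 7.2 lists them under withdrawal. In the worked case with half exiting, that would give 22% instead of 56%. The documents do not support that reading:
- Protocol 7.1 does not list access among reasons to stop study intervention, and 7.2 lists it separately from stopping study intervention.
- Footnote e of the Schedule of Activities describes early withdrawal as before Week 104 or end-of-study, and access exits have an end-of-study visit.
- Protocol 4.4 and SAP 5.2 make them completers.
- Protocol 6.6 ends sponsor supply for Week 104 completers too, so treating end of supply as discontinuation would fail everyone.

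A reader might also infer that the curve from parent-study remission is invalid. It is not. It describes enrolled participants, and the analysis set is stated in SAP section 4. It needs only a note that it is conditional on enrolment.

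**Conclusion.** The concern holds as a minor one. With access exits counted as successes, the crude proportion mixes unequal follow-up and tends to overstate the Week 104 composite: by about 1 to 3 points if a tenth exit for access, 3 to 7 if a quarter and 6 to 14 if half. With no access exits there is no difference. These sizes rest on assumed constant hazards and on exits that are uniform in time and unrelated to outcome; the documents supply no rates. Neither the success-per-time rate nor the planned Kaplan-Meier percentiles give the missing Week 104 value. The study is single-arm and descriptive, so no hypothesis test is affected.

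**What to change.** Keep the crude proportion as descriptive and add to SAP 5.4.1.2:
- A Kaplan-Meier estimate, with 95% CI, of freedom from relapse or discontinuation of any study-intervention component at Week 104 of the extension.
- Origin Day 1 of the extension; set: parent Week 8 remitters with no relapse before Day 1. Report how many had such a relapse, and state that the estimate is conditional on being relapse-free at Day 1. It will therefore not match a proportion that counts those people as failures.
- Access exits censored at their end-of-study visit, a Week 104 visit inside its window counted as follow-up to Week 104, and numbers at risk shown.
- Optionally, relapse-only cumulative incidence with other discontinuation as a competing event. In the worked case this is (0.3/0.4) × (1 − 0.449) = 41%, against 1 − exp(−0.6) = 45% if discontinuations are censored.

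Add one sentence to 5.4.1.1 confirming that an access exit is not discontinuation of study intervention. Note that the curve from parent-study remission is conditional on enrolment. Do not use the success-per-time rate to account for unequal follow-up.

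**Cost.** SAP text and one further analysis on data already collected. The interval widens when access exits are common. In simulation of the worked case with half exiting, mean widths are 23 points (Kaplan-Meier) against 20 (Clopper-Pearson) at n = 100, 32 against 28 at n = 50, and 40 against 37 at n = 30. About n × 0.5 × 0.449 = 22, 11 and 7 people remain at risk at Week 104. At a quarter exiting, widths are about equal. The documents do not give the number of Week 8 remitters. Censoring assumes that launch timing is unrelated to outcome, which may fail if relapse differs by country.
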